Since patients were distributed across cohorts, the required number of patients in each cohort was established in accordance with the recommendations of the U.S. Department of Health and Human Services Food and Drug Administration (FDA) regarding the safety, pharmacokinetics and effectiveness studies of immunoglobulin in primary immunodeficient conditions. According to that guidance document, the optimal number of patients in subgroups for pharmacokinetic assessment (adult patients) ranges from 6 to 12, to obtain a reliable assessment of variability. Considering these recommendations, the number of patients in the cohorts for adult patients was determined to be between 8 and 10.

During the Data Analysis phase, it is envisaged to allow assessment of patients based on the identified covariates.

Study phases.

The patient/their legally authorised representative/the patient's parents should sign informed consent.

After signing the informed consent, the screening examinations are performed, and patient's eligibility is assessed against inclusion/non-inclusion criteria.

During the screening phase, verification of PID diagnosis is required (according to the ESID criteria) based on source documentation data (see Section 6.3.3 of the Protocol).

- **Screening period:**

- Visit 1: Day 0 – signing the ICF, determination of IgG levels*
- Visit 2: Day 21–28 (range: 21–28 days) – determination of IgG levels*
- Visit 3: Day 42–56 (range: 21–28 days) – determination of IgG levels*. Determination of pharmacokinetic parameters of BIOVEN in patients aged over 18 years who have previously received therapy with BIOVEN (7 blood sampling points additionally)

*For the group of patients from Cohorts A and B who have already received SCIG or IVIG, an assessment of monthly threshold IgG levels is performed during prior treatment (the prior treatment continues).

The screening period is different across different cohorts:

- For Cohort A, patients who have previously received SCIG are required to undergo Visits 1 and 2 of the screening period. In the event of meeting the criterion “total serum IgG level ≥ 5 g/L – as confirmed by the results of at least two (2) measurements performed immediately prior to the subsequent administration of SCIG after signing the ICF”, the patient proceeds to treatment with the IMP BP-SCIG 20%, starting from Cycle 1. If the criterion is not met, then Visit 3 is performed.
- For Cohort B, patients who have previously received IVIG:

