The assessment of threshold (trough) IgG levels is to be performed in at least 40 patients enrolled in the CT; of these, 20 subjects must be children or adolescents with an appropriate age distribution for this patient group. The trough levels of the IgG from the investigational medicinal product must be assessed after 4 months of treatment with the IMP, prior to the next infusion, once every 4 weeks (once per month/treatment cycle) over 6 months.

The obtained monthly trough IgG levels shall be compared with the trough levels for at least two prior infusions of the previous SCIG or IVIG product. Alternatively, for treatment-naïve patients, a descriptive comparison with published literature (if available) is performed.

Phase of IVIG pharmacokinetic assessment

This phase includes patients older than 18 years who had been receiving previous therapy with the medicinal product BIOVEN prior to their study entry and, accordingly, throughout the screening period.

PK will be assessed through an additional sampling of 3.5 mL of venous blood (per one sampling, a total of 8–9 sampling time points) for subsequent determination of patient's levels of plasma immunoglobulin in the samples over 21–28 days after the infusion of BIOVEN. The total volume of venous blood for the entire IVIG PK assessment per one patient is 28–31.5 mL.

The data obtained during the phase of BIOVEN pharmacokinetics will be used to confirm or recalculate the dose adjustment factor for switching from IVIG to the IMP.

The assessment begins at Visit 3 of the screening period (see Table 4.2.3 Pharmacokinetic assessment of IVIG – BIOVEN). The time of blood sampling is documented.

Phase of IMP BP-SCIG 20% pharmacokinetic assessment

This phase includes at least 20 patients older than 18 years who had been receiving the investigational medicinal product for at least 4 months, and did not have any severe bacterial complications during the trial.

PK will be assessed through an additional sampling of 3.5 mL of venous blood (per one sampling, a total of 8 sampling time points) for subsequent determination of patient's levels of plasma immunoglobulin in the samples over 7 days after the infusion of the IMP BP-SCIG 20%. The total volume of venous blood for PK assessment for one patient is 28 mL.

The assessment is performed at Week 21 (see Table 4.2.2 – Pharmacokinetic assessment of the IMP). The time of blood sampling is documented.

Study phases. Follow-up and completion of the study

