¹⁰ Total IgG is determined using the nephelometry method for PK assessment, i.e. the threshold level on Day 7 post-infusion of the IMP BP-SCIG 20% in at least 40 patients, of whom no less than 20 subjects are children and adolescents younger than 18 years;

¹¹ PK parameters are determined using the nephelometry method at Visit 3 (7 blood sampling points additionally) in adult patients receiving previous therapy with BIOVEN, and at Visit C6W21 (7 blood sampling points additionally), in at least 20 adult patients treated with the IMP BP-SCIG 20% for at least 4 months with no severe bacterial complications and who have signed Informed Consent to participate in the pharmacokinetic assessment;

¹² Specific gravity; pH, glucose, microscopic sediment examination (red blood cells, white blood cells, casts, crystals, bacteria, fungi);

¹³ The test (HCG) can be performed at any visit during the study if a female patient reports a potential pregnancy;

Table 4.2.1. Schedule of Study Procedures (Continued)

Visits	Cycle 8 Weeks 29–32		Cycle 9 Weeks 33–36		Cycle 10 Weeks 37–40		Cycle 11 Weeks 41–44		Cycle 12 Weeks 45–48		Cycle 13 Weeks 49–52		Visit 17	Unscheduled
Study phase	Treatment period												Follow-up	-
Procedures / Time point	Week 29 (C8W29)	Weeks 30–32 (C8W30– C8W32)	Week 33 (C9W33)	Weeks 34–36 (C9W34– C9W36)	Week 37 (C10W37)	Weeks 38–40 (C10W38– C10W40)	Week 41 (C11W41)	Weeks 42–44 (C11W42– C11W44)	Week 45 (C12W45)	Weeks 46–48 (C12W46– C12W48)	Week 49 (C13W49)	Weeks 50–52 (C13W50– C13W52)	Week 53	Actual Date
Informed Consent signing														
Collection of demographics														
Collection of anthropometrics ¹⁴	x		x		x		x		x		x			x
Collection of medical history ¹⁵														x
Data on antibiotic therapy and concomitant therapy	●	#	●	#	●	#	●	#	●	#	●	#	●	x
Presence of infections	●	#	●	#	●	#	●	#	●	#	●	#	●	x
Physical examination ¹⁶	x		●		x		x		●		x		●	x
Vital signs ¹⁷	●		●		●		●		●		●		●	x
Chest X-ray/CT/MRI											●			
12-lead ECG;														
Complete blood count ¹⁸	●						●						●	x
Serum chemistry ¹⁹	●						●						●	x
Direct Coombs' test (antiglobulin test) ²⁰	x		x		x		x		x		x		x	x
Haptoglobin level ²¹	x		x		x		x		x		x		x	x

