For Cohort C, newly diagnosed (treatment-naïve) patients are required to undergo Visit 1 of the screening period; if meeting inclusion/non-inclusion criteria, the patient proceeds to treatment with the IMP BP-SCIG 20%, starting from Cycle 1.

Table 4.2.2 Schedule of Procedures at Week 21 – Pharmacokinetic assessment of the IMP

Structure of PK assessment*		
No.	PK point	Description
1	PK0 (pre-administration)	Before IMP administration (10–30 min prior)
2	PK1 (30 min)	30 minutes after IMP administration (± 10 min)
3	PK2 (3 hours)	3 hours after IMP administration (± 30 min)
4	PK3 (1 day)	24 hours after IMP administration (± 5 h)
5	PK4 (2 days)	48 hours after IMP administration (± 5 h)
6	PK5 (3 days)	72 hours after IMP administration (± 5 h)
7	PK6 (4 days)	96 hours after IMP administration (± 5 h)
8	PK7 (7 days, threshold)	After 7 days (± 5 h), before the next administration of the IMP

* – The points for pharmacokinetic assessment of BP-SCIG 20% were selected in accordance with the available data on achieving Cmax following subcutaneous administration of the MPs belonging to the subcutaneous immunoglobulin category, and for the purpose of clear demonstration of differences in concentration-time curves for IVIG and SCIG.

Table 4.2.3. Schedule of procedures at Visit 3 – Pharmacokinetic assessment of IVIG

Structure of PK assessment**		
No.	PK point	Description
1	PK0 (pre-administration)	Before administration of BIOVEN (10–30 min prior)
2	PK1 (15 min)	15 minutes after administration of BIOVEN (± 10 min)
3	PK2 (1 hour)	1 hour after administration of BIOVEN (± 15 min)
4	PK3 (1 day)	24 hours after administration of BIOVEN (± 5 h)
5	PK4 (3 days)	72 hours after administration of BIOVEN (± 5 h)
6	PK5 (7 days)	7 days after administration of BIOVEN (± 5 h)
7	PK6 (14 days)	14 days after administration of BIOVEN (± 5 h)
8	PK7 (21 days)	21 days after administration of BIOVEN (± 5 h)
9	PK8 (28 days)	28 days after administration of BIOVEN (± 5 h) (where applicable***)

**The points for pharmacokinetic assessment of BIOVEN were selected based on previous PK studies of BIOVEN.

***Interval between the administrations (every 21–28 days) of BIOVEN, used as a prior therapy, is determined individually for each patient in accordance with the approved instructions for medical use.

4.3. Randomisation and blinding.

No randomisation or blinding is used in this clinical trial.

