5.1. Inclusion Criteria

Table 5.1.1 – Inclusion criteria for CT subjects

No.	Inclusion criterion
1.	a signed informed written consent of the patient/patient's parents or legally authorised representative to take part in the study;
2.	children from 0 to 18 years of age, of both sexes; or adult patients: males and females older than 18 years;
3.	a diagnosis of primary immunodeficiency with impaired antibody production document-supported according to the ESID criteria, requiring replacement therapy with immunoglobulins;
4.	patients with a body weight of no less than 9.1 kg;
5.	patients who received replacement therapy with intravenous immunoglobulin (IVIG) products at intervals from 21 to 28 days at the dose of 0.4–0.8 g/kg, for at least 4 months prior to the start of the study and have total serum IgG levels ≥ 5 g/L*, which is confirmed by the results of no less than 2 measurements performed immediately before the scheduled IVIG administration after signing the ICF, or patients who received replacement therapy with subcutaneous immunoglobulin (SCIG) products at the dose of 0.4–0.8 g/kg per month, for at least 4 months prior to the start of the study, and have total serum IgG levels ≥ 5 g/L*, based on the results of no less than 2 measurements performed immediately before the scheduled SCIG administration after signing the ICF; or patients with a newly established diagnosis of PID who have not yet received replacement therapy with IgG products (treatment-naïve patients) and have a serum IgG level ≤ 4 g/L;
6.	absence of episodes of serious bacterial infections (bacteraemia or sepsis, bacterial meningitis, osteomyelitis/septic arthritis, bacterial pneumonia, visceral abscess) while taking the previous medicinal product and absence of episodes of hospitalisation for at least 3 months prior to inclusion in the study and during the screening period (prior to the first administration of the IMP BP-SCIG 20%);
7.	a negative pregnancy test (in female patients with childbearing potential); readiness to use reliable methods of contraception throughout the study period;
8.	patient's ability, in the Investigator's judgement, to comply with all the requirements of the study protocol.

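### BIOVEN PK samples are fixed at days 21 and 28, so patients on 22–27-day intervals have no defined end-of-interval PK sample; the count of 7 extra draws also conflicts with the sampling table

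*Protocol*

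**What the plan says.** **Eligible intervals.** Protocol Section 5.1, criterion 5, admits patients on "intravenous immunoglobulin (IVIG) products at intervals from 21 to 28 days". The note under Table 4.2.3 adds that the interval between administrations "of BIOVEN, used as a prior therapy, is determined individually for each patient in accordance with the approved instructions".

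**Sampling times.** Table 4.2.3, repeated in Section 6.3.9, ends with PK7, "21 days after administration of BIOVEN (± 5 h", and PK8, "28 days after administration of BIOVEN (± 5 h) (where applicable" (bracketed text cut at the end of each quote). In Table 4.2.2, by contrast, the last sample for the investigational product is placed before the next dose.

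**Use of the data.** Section 9.7 defines AUC0-t as running to the last quantifiable blood sample. Section 9.6 lists AUC-t first among the main PK parameters and compares it with BIOVEN. Section 3 makes a non-inferior steady-state AUC part of the primary objective. Section 4.2 uses the BIOVEN data to confirm or recalculate the conversion factor of 1.37.

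**Draw counts.** Table 4.2.1, footnote 11, says PK parameters are determined "at Visit 3 (7 blood sampling points additionally) in adult patients receiving previous therapy with BIOVEN". Footnote 23 and the Visit 3 entry in Section 4.2 also say "7 blood sampling points additionally". The description of the IVIG PK phase in Section 4.2 gives "a total of 8–9 sampling time points" and 28–31.5 mL. Section 6.3.13 takes PK0 from the Visit 3 trough sample and lists PK1 to PK8 with volumes.

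**The concern.** The sampling grid suits intervals of exactly 21 or 28 days, but eligibility and the table note allow everything between. For an interval of 22–27 days, the day-21 sample comes before the interval ends and the day-28 sample does not match it. With AUC0-t ending at the last sample, the BIOVEN exposure of such a patient would be measured over less than one dosing interval.

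That exposure is the comparator for part of the primary objective and the basis for checking the conversion factor. Adult cohorts are planned at only 8–10 patients (Sections 4.2 and 9.2), so a few shortened profiles could shift the comparison. The investigational product's profile does end at its next dose, so the two sides of the comparison close on different rules.

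The conflicting draw counts are a separate matter of site instructions: the main schedule and the PK table disagree for a 28-day patient.

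**Working it through.** **1. The plan's own volumes.** At 3.5 mL per draw:
- PK0–PK7: 8 × 3.5 = 28.0 mL.
- PK0–PK8: 9 × 3.5 = 31.5 mL.

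This reproduces the stated 28–31.5 mL. Beyond PK0, that is 7 draws through PK7 and 8 through PK8. Section 6.3.13 agrees: 7 + 6 × 3.5 = 28.0 mL for PK1–PK8, plus 3.5 mL for PK0. A count of 7 additional draws fits a 21-day interval and is one short for a 28-day interval.

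**2. Coverage when the last sample is day 21.** The protocol gives no IgG half-life, so I assume mono-exponential decline with a half-life h of 21 to 35 days. With interval τ:
- AUC ratio = AUC(0–21)/AUC(0–τ) = (1 − 2^(−21/h)) / (1 − 2^(−τ/h)).
- Ratio of average levels = AUC ratio × τ/21.

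Example, h = 21, τ = 27: 0.5000/0.5898 = 0.848; × 27/21 = 1.090.

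Example, h = 35, τ = 27: 0.3402/0.4142 = 0.822; × 27/21 = 1.056.

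| τ (days) | AUC ratio, h = 21 | AUC ratio, h = 35 | Average-level ratio, h = 21 | Average-level ratio, h = 35 |
|---|---|---|---|---|
| 22 | 0.969 | 0.963 | 1.015 | 1.009 |
| 24 | 0.914 | 0.899 | 1.044 | 1.028 |
| 27 | 0.848 | 0.822 | 1.090 | 1.056 |

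Over 22–27 days, AUC to day 21 is thus 82–97% of the interval AUC. Divided by 21 days, it overstates the average level by 1–9%.

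**3. Sensitivity to the model.** A steady-state biexponential profile was also run, assuming a terminal half-life of 21, 30 or 40 days, a distribution half-life of 2 days and a 40% distribution share. AUC coverage was 96–97% at τ = 22, 90–92% at τ = 24 and 82–86% at τ = 27. The average level was overstated by 1–2%, 3–5% and 6–10% respectively. The conclusion does not depend on the simpler model.

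**4. Effect of closing the interval.** In the same biexponential runs, adding a concentration at τ (a sample there, or the steady-state PK0 used as that value) brought the trapezoidal AUC to 1.004–1.009 times the true interval AUC. Log-linear extrapolation from days 14–21 gave the same range, so the error falls to within about 1%.

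**The case against.** Much of the case on the other side stands.

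- **Trough.** A reader might infer that the end-of-interval trough is never measured. That is not so. PK0 is drawn before the Visit 3 infusion and, in a patient treated for at least 4 months, gives the trough of the preceding interval. The trough comparison uses pre-infusion samples of this kind, not day 21.
- **Direction.** A reader might infer a bias in one known direction. The documents do not support that: raw AUC to day 21 understates BIOVEN exposure, while dividing by 21 days overstates the average level. The protocol does not say which is used.
- **28-day patients.** A reader might infer that they lose their last sample. PK8 is scheduled in Table 4.2.3 and Section 6.3.9, has a volume in Section 6.3.13, and is covered by the 8–9 points in Section 4.2. Only the count conflicts.
- **Post-dose PK8.** A reader might infer that PK8 would be drawn after the next dose in patients on shorter intervals. The note making PK8 conditional on the patient's own interval points to its simply not being drawn.
- **Repair in analysis.** A 7-day profile cannot be set against a 21–28-day profile without some standardisation, and an analysis plan not shown here may supply it. PK0, the documented sampling times and an elimination constant per patient would allow it.
- **Scope.** The dose formula divides by the number of weeks between infusions, which suggests that many patients are on 3 or 4 weeks.

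What remains is what the protocol itself fixes: sampling days that do not match the eligible intervals, and an AUC ending at the last sample. It does not assign PK0 as the closing value. Table 4.2.1 requires a pre-dose IgG sample at the first dose of the investigational product, but does not list it as a PK point or time it from the last BIOVEN infusion. An analysis rule can approximate the missing concentration but cannot measure it, and it cannot reconcile conflicting site instructions.

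**Conclusion.** The concern holds in limited form. As written, adult BIOVEN patients on 22–27-day intervals have no PK sample defined at the end of the sampled interval, and their AUC0-t stops at day 21. Under an assumed mono-exponential half-life of 21–35 days, that AUC covers about 82–97% of the interval, or gives an average level about 1–9% too high if divided by 21 days.

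Whether the comparison is biased, and which way, depends on the normalisation and on how many patients fall between 21 and 28 days; the protocol states neither. The draw count of 7 is a separate inconsistency: right for 21-day intervals, one short for 28-day intervals. Both deserve correction because this AUC is the comparator for part of the primary objective and for the conversion factor, and the remedy is small.

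**What to change.** 1. In Table 4.2.3 and Section 6.3.9, define the last BIOVEN PK sample as taken immediately before the next administration, at the patient's own interval, in parallel with PK7 of Table 4.2.2.
2. In Section 9.7, compute BIOVEN AUC from 0 to that interval using actual sampling times. If the last sample is missing, use the steady-state PK0 as the end-of-interval value or log-linear extrapolation, and state which.
3. In the Visit 3 entry of Section 4.2 and in Table 4.2.1, footnotes 11 and 23, give 7 additional samples for 21-day intervals and 8 for longer ones.

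The cost is one re-timed sample per affected patient, within the stated 31.5 mL, plus wording changes in the places named. No dose or dosing interval changes.

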4.4. IMP description and labelling

Name: BP-SCIG 20% (Human normal immunoglobulin for subcutaneous administration)

Active ingredient:

Human normal immunoglobulin (including immunoglobulin G (IgG) $\geq 95\%$) 1 mL of the product contains 0.2 g;

The following batches of the investigational medicinal product will be used as part of this clinical study:

- 24S5001R, 50 mL;
- 24S5002R, 50 mL;
- 24S5003R, 50 mL;
- 24S05001R, 5 mL;
- 24S05002R, 5 mL;
- 24S05003R, 5 mL.

Labelling of the investigational product

The necessary information shall be provided in the official language.

The investigational medicinal product must be labelled with the following symbols and fields:

Secondary packaging:

- name of the legal entity acting as the clinical trial sponsor, location and phone number of the clinical trial sponsor;
- pharmaceutical form, route of administration, number of dosage units, name/identifier and strength/activity;
- batch number;
- clinical trial code allowing identification of the trial, clinical trial site, clinical trial sponsor;
- identification number of the study subject;
- surname and first name of the Responsible Investigator/Investigator;
- “For clinical trial use only” labelling;
- storage conditions;
- period of use (“use before”, expiry date, etc.), specified in the Month/Year format and in a manner that excludes ambiguity of interpretation;
- “Keep out of reach of children” labelling.

Instructions for Use are specified in the “Guidance on home-based administration of BP-SCIG 20% for adults and children”.

Immediate packaging:

- name of the legal entity acting as the clinical trial sponsor;
- pharmaceutical form, route of administration, number of dosage units, name/identifier, and strength/activity;
- batch of the investigational medicinal product;
- clinical trial code allowing identification of the trial, clinical trial site, clinical trial sponsor;
- identification number of the study subject.

LABELLING TO APPEAR ON THE OUTER PACKAGING OF THE MEDICINAL PRODUCT

BP-SCIG 20%, Human normal immunoglobulin for subcutaneous administration, solution for injection 5 mL in vials No. 1

SECONDARY PACKAGING**1. NAME OF THE MEDICINAL PRODUCT**

BP-SCIG 20%, Human normal immunoglobulin for subcutaneous administration, solution for injection

2. STATEMENT OF ACTIVE INGREDIENT(S)

Composition: 1 mL of the product contains:

Active ingredient: Human normal immunoglobulin 200 mg/mL (including immunoglobulin G (IgG) no less than 95 %)

Distribution of immunoglobulin G subclasses in the product:

IgG₁: 65.6 %, IgG₂: 22.1 %, IgG₃: 10.8 %, IgG₄: 1.5 %

The maximum content of immunoglobulin A is 100 µg/mL.

3. LIST OF EXCIPIENTS

Excipients: glycine; water for injection

4. PHARMACEUTICAL FORM AND NUMBER OF DOSAGE UNITS PER PACKAGE

Solution for injection 20 %

1 vial 5 mL

Protein concentration: 200 mg/mL

5. METHOD AND ROUTE OF ADMINISTRATION

For subcutaneous use only.

6. SPECIAL WARNING THAT THE MEDICINAL PRODUCT MUST BE STORED OUT OF THE SIGHT AND REACH OF CHILDREN

Keep out of the reach of children.

7. OTHER SPECIAL WARNING(S)

Sterile. Do not administer intravenously!

8. EXPIRY DATE

Available

9. STORAGE CONDITIONS

Store in the original package to protect from light at a temperature of 2°C to 8°C.

10. SPECIAL PRECAUTIONS FOR DISPOSAL OF UNUSED MEDICINAL PRODUCTS OR WASTE MATERIALS DERIVED FROM SUCH MEDICINAL PRODUCTS, IF APPROPRIATE**11. NAME AND ADDRESS OF THE MANUFACTURER AND/OR APPLICANT**

BIOPHARMA PLASMA LLC

Legal address and place of business:

[name]

[contact]

12. MARKETING AUTHORISATION NUMBER**13. BATCH NUMBER***Available***14. GENERAL CLASSIFICATION FOR SUPPLY**

Prescription only medicine

15. IF THE MEDICINAL PRODUCT IS INDICATED FOR SELF-TREATMENT, INFORMATION FOR ITS USE*Specified in the "Guidance on home-based administration of BP-SCIG 20% for adults and children"***16. INFORMATION IN BRAILLE****17. OTHER INFORMATION***BIOPHARMA PLASMA, LLC Logo**Bar-code*

FOR CLINICAL STUDY USE

Study Code: 2024-SCIg-BP

Study subject No.: _____

Investigator: _____

LABELLING TO APPEAR ON THE OUTER PACKAGING OF THE MEDICINAL PRODUCT**BP-SCIG 20%, Human normal immunoglobulin for subcutaneous administration, solution for injection 50 mL in vials No. 1****SECONDARY PACKAGING****1. NAME OF THE MEDICINAL PRODUCT**

BP-SCIG 20%, Human normal immunoglobulin for subcutaneous administration, solution for injection

